9.3.2.2 Secondary outcomes

We will assess drug discontinuation as a secondary outcome. Pirfenidone or nintedanib discontinuation will be defined as presence of sixty or more days gap in refilling a prescription of the drug (sixty days gap counted from the date of last fill plus the days of supply for the fill). The date of last fill plus the days of supply for the fill (typically 30 days) will be designated as date of discontinuation, and time to discontinuation will be calculated as time between date of discontinuation and index date (only for patients who discontinue the drug). We will calculate the percentage of patients who discontinue each drug in first 6- and 12-months post-index period. As a sensitivity analysis, we will calculate drug discontinuation using 30 days and 90 days as allowed gap between the scripts (vs. 60 days)

We will also assess how many patients initiate either of the antifibrotic drugs (including the same drug the patient has discontinued) during the follow-up time post discontinuation of their index drug. We will separately assess initiation of the index drug vs. initiation of the other antifibrotic agent.

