The main outcome of our study will be incidence of dose reduction/interruption, calculated separately for pirfenidone and nintedanib. For each patient, average daily dose will be calculated in pre-specified time-periods (for example – the first 6 months, the first 12 months, and the average daily dose calculated separately in each month since drug initiation) (more details in section 2.6). Incidence of dose reduction/interruption will be defined as average daily dose not following the prescribing information (PI). According to the PI, the daily dose of pirfenidone is 2403 mg [13], hence the study will consider average daily dose less than 2165 mg (90% of PI dose) as dose reduction for pirfenidone [12]. For nintedanib, the daily dose allowed under prescriber information is 200 mg [14], hence less than 200 mg will be considered a dose reduction for nintedanib patients. As a secondary outcome, we will also assess drug discontinuation during first 6 and 12 months separately for pirfenidone and nintedanib and will be defined as a gap of at least 60 days in filling of prescription (a gap of 60 days after the prescription date + days of supply for the current prescription). In a sensitivity analysis, we will explore 30- and 90- days gap as a definition for drug discontinuation. As this is a descriptive study, assessment of the dose reduction and discontinuation for both drugs will be considered separately, and only descriptively, without any direct comparison between the two cohorts.

NIS Protocol Page 16 of 36

Study number: 1199-0526 Document number: c41847952-01

Proprietary confidential information © 2023 Boehringer Ingelheim International GmbH or one or more of its affiliated companies

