9.2 SETTING

9.2.1 Study sites

We will use administrative health insurance claims data from the Optum Research Database (ORD) for the period of October 1, 2013 through end of data availability (currently September 30, 2021). The ORD contains enrollment information, as well as fully-adjudicated medical claims and pharmacy claims for commercial enrollees and MAPD beneficiaries. In 2018, the ORD included 14.3 million commercial enrollees with medical and pharmacy benefits and 4.3 million beneficiaries with Medicare Part C (commonly referred to as the Medicare Advantage program). Medicare Advantage beneficiaries choose to receive all of their health care services through a provider organization in lieu of Medicare Part A/B coverage (commonly referred to as Medicare Fee for Service). These plans are referred to as MAPD when combined with Medicare Part D coverage. The average enrollment duration was 31.4 and 37.3 months for commercial enrollees and MAPD enrollees, respectively. Underlying information is geographically diverse across the United States and enrollees are fairly representative of the U.S. population. Medicare beneficiaries retain a single identifier within the system and can be tracked as they change plans, or as they disenroll and reenroll over time.

Claims for pharmacy services are typically submitted electronically by the pharmacy at the time prescriptions are filled. The claims history is a profile of all outpatient prescription pharmacy services provided and covered by the health plan. Pharmacy claims data include drug name, dosage form, drug strength, fill date, days of supply, financial information, and de-identified patient and prescriber codes, allowing for longitudinal tracking of medication refill patterns and changes in medications. Pharmacy claims are typically added to the research database within six weeks of dispensing.

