9.3.2 Outcomes

9.3.2.1 Primary outcome

The main outcome measure of our study is the incidence of dose reduction/interruption, calculated separately for each drug. For calculating the primary outcome, we will first need to calculate the average daily dose of pirfenidone and nintedanib after drug initiation (post-index period). Specific details of calculations are —

Average daily dose

Average daily dose for each patient will be calculated by taking the average of total drug intake (tablet strength * number of doses) during the time between index date to the date of drug discontinuation

```
Average \ Daily \ Dose \\ = \frac{\sum_{0}^{n}(Tablet \ Strength*number \ of \ tablets \ in \ a \ Rx \ fill)}{Time \ of \ follow - up \{(Date \ of \ discontinuation) - Index \ Date\}} Where n = number of fills a patient has received for pirfenidone/nintedanib
```

- We will calculate average daily dose of pirfenidone and nintedanib separately for each month in post-index period (month 1 to 12) and will also calculate for cumulative periods of 6 months and 12 months. For all calculations, censoring events will be taken into account, with patient censored at the date of drug discontinuation, or end of 12 months.
- Six and twelve months average daily dose categories For the average daily dose calculations in cumulative periods, we will be dividing the patients in following 4 categories
 - 1) Dose strength less than 50%
 - 2) Dose strength between 51% to 66%
 - 3) Dose strength between 67% to 90%
 - 4) Dose strength above 90%

Incidence of Dose Reduction and/or temporary dose interruption

Once average daily dose is calculated for each month post-index (month 1 to 12), incidence of dose reduction/interruption will be calculated as presence of average daily dose $\leq 90\%$ dose strength (for pirfenidone) or $\leq 66.67\%$ dose strength (for nintedanib), as per the PI [12 – 14]. Patients will be required to have the dose reduction for at least for 60 days, to make sure that the dose reduction is not temporary.

In a sensitivity analysis, we will also evaluate temporary dose reductions, i.e., dose reduced to below the above defined dose strength only for 1 month.

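### Discontinuation is timed from the last fill's own supply, so drug left over from early refills is ignored in the stop date but counted in the average dose

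*Combined protocol and SAP*

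**What the plan says.** Section 9.3.2.2 calls a patient discontinued after 60 days or more without a refill, with the "sixty days gap counted from the date of last fill plus the days of supply for the fill". It then fixes the stop date at the same point: "The date of last fill plus the days of supply for the fill (typically 30 days) will be designated as date of discontinuation". Section 9.1 gives the same rule, "a gap of 60 days after the prescription date + days of supply for the current prescription", and the abstract (Section 4) repeats it. The sensitivity analyses replace 60 days by 30 and 90 days; nothing says that the starting point of the count changes. No section shifts overlapping supply forward from one fill to the next.

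The stop date is used in three places:
- Time to discontinuation: "time to discontinuation will be calculated as time between date of discontinuation and index date" (Section 9.3.2.2).
- Status: "We will calculate the percentage of patients who discontinue each drug in first 6- and 12-months post-index period" (Section 9.3.2.2).
- Average daily dose (Section 9.3.2.1): strength times tablets, summed over all fills, divided by the time from index to discontinuation, "with patient censored at the date of drug discontinuation, or end of 12 months".

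Section 9.9 warns that daily dose derived from fills may differ from true intake. It does not mention early refills, leftover supply or the stop date.

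**The concern.** The rule restarts the supply clock at every fill. When a 30-day supply is refilled a few days early, the unused days drop out of the clock, and they accumulate over repeated early refills. After the last fill, those days are treated as days without drug.

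The plan also handles the same tablets in two ways within one calculation. The dose numerator counts them as drug used, while the denominator stops before the days they would cover. The issue therefore reaches the average daily dose under the primary aim as well as the secondary outcome.

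At stake are stop dates that are too early, a mean time to discontinuation that is too short, and cumulative doses that are too high in discontinuers. Some patients would also change 6- or 12-month status. A patient wrongly called discontinued who then refills would be counted as re-initiating the index drug (Section 9.3.2.2) and would be lost from the analysis of patients who never discontinue (Section 9.3.2.1).

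**Working it through.** The plan gives no figure to reproduce, so the rule is applied to simple fill histories.

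**Inputs.** Section 9.3.2.2 gives the anchor (last fill plus its supply), the typical 30-day supply and the 60-day gap, with 30 and 90 days as sensitivity. Section 9.3.2.1 gives the dose formula. These are assumptions, not in the documents: every fill is 30 days, every refill is k days early, leftover drug is taken after the last fill, 6 months is 183 days, 12 months is 365 days, and status is decided by the stop date.

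**Formulas**, with n fills and index at day 0:
- Stop under the plan = (n − 1)(30 − k) + 30
- End of supply with carry-over = 30n
- Days dated early, s = k(n − 1)
- Dose under the plan, relative to the dose supplied per day = 30n / [(n − 1)(30 − k) + 30]

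**Dating and dose, six fills** (carry-over end is day 180 throughout):

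| k | Plan stop (day) | Days early | Dose, full regimen | Dose, assumed 80% regimen |
|---|---|---|---|---|
| 0 | 150 + 30 = 180 | 0 | 180/180 = 100% | 80% |
| 3 | 135 + 30 = 165 | 15 | 180/165 = 109% | 144/165 = 87% |
| 5 | 125 + 30 = 155 | 25 | 180/155 = 116% | 144/155 = 93% |
| 7 | 115 + 30 = 145 | 35 | 180/145 = 124% | 144/145 = 99% |

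With twelve fills the stop is 33 days early at k = 3 (day 327 instead of 360) and 55 days early at k = 5 (day 305 instead of 360).

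With carry-over, the six-fill rows return to 100% and 80%. At k = 5 the 80% regimen moves from the 67–90% category to the one above 90%; at k = 3 it does not.

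**Status.** It can change in two ways.
1. The moved date crosses a cutoff. Seven fills at k = 5 stop at day 6 × 25 + 30 = 180 under the plan and day 210 with carry-over, so 6-month status changes. Thirteen fills at k = 3 stop at day 12 × 27 + 30 = 354 against day 390, so 12-month status changes.
2. The patient resumes within the extra stock days. With s = 25, a refill 60 to 84 days after the plan's stop date counts as following a discontinuation, although only 35 to 59 days were uncovered.

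**Full cover through the gap.** This needs s of at least the gap length. For 60 days that is 13 fills at k = 5 (12 × 5 = 60) or 10 fills at k = 7 (9 × 7 = 63). For the 30-day sensitivity gap, seven fills at k = 5 are enough (6 × 5 = 30).

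**Where the rule is not the cause.** A patient who continues at k = 5 has 15 fills by day 350 and computes to 450/365 = 123% at 12 months with or without carry-over. For seven fills at k = 5 the moved date (day 210) lies past the 6-month window, so the 6-month figure with carry-over is still 210/183 = 115%.

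**The case against.** The rule is explicit, consistent across three sections and easy to reproduce. A 90-day gap already absorbs up to 30 days of hidden stock for status. Neither rule observes intake: carry-over assumes leftover tablets are taken, which is a weak assumption in a study of dose reduction, interruption and stopping. The documents give no early-refill rate, and with on-time refills the bias is zero. All of this stands, and it limits the size of the point. It does not remove it, because changing the gap length does not correct the date, and the dose formula itself treats the leftover tablets as used.

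A reader might go further and infer that patients who still hold drug are commonly classed as stopped. The documents do not support that for the 60-day rule. With the stop inside the 6-month window (last fill by day 153), 60 days of stock needs k of at least 9: k = 8 gives 6 × 8 = 48. At 12 months (last fill by day 335) it needs k of at least 5: k = 4 gives 12 × 4 = 48. A regular early refiller also does not trigger the rule while still refilling; the patient must then go 90 days from the last fill without another.

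Nor should every average dose above 100% be blamed on this rule, as the last two examples in the working show. And nothing in the documents says that early refillers are more adherent than others.

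**Conclusion.** The point holds in a limited form and is worth correcting. If leftover drug is taken, the stop date is early by k × (fills − 1) days, which for six fills is 0 to 25 days for k from 0 to 5. For discontinuers whose moved date stays inside the window, cumulative dose is overstated by the same mechanism: 109% at k = 3 and 116% at k = 5. Most discontinuers keep their status. It changes only if they resume within the extra stock days or the moved date crosses 6 or 12 months. The 30-day sensitivity analysis is the most exposed to false stops.

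The sizes rest on assumed 30-day fills and regular early refills. The number of patients affected cannot be derived from the documents. The effect on the month-by-month dose-reduction incidence was not calculated.

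**What to change.** Define end of supply with carry-over: where same-strength fills of the index drug overlap, move the later supply forward to start when the earlier one ends, and state any cap. Use that one date for the 30-, 60- and 90-day gaps, the discontinuation date and the average-daily-dose denominator. Report the present no-carry-over rule alongside as a sensitivity analysis. At minimum, keep the present rule as the main analysis and pre-specify the carry-over version as a sensitivity analysis.

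No new data are needed. Section 9.2.1 confirms that "Pharmacy claims data include drug name, dosage form, drug strength, fill date, days of supply" are captured. The cost is a short change to the text and the programming. The downside is that stops are dated too late for patients who do not use leftover drug; reporting both versions shows how much that matters. Carry-over will not bring doses below 100% for patients who continue refilling early or whose moved date passes the window end, and the report should say so.

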9. RESEARCH METHODS

9.1 STUDY DESIGN

This study will be a retrospective cohort, descriptive study of patients with idiopathic pulmonary fibrosis (IPF). Patients with IPF who initiated either pirfenidone or nintedanib between October 2014 to September 2021 will be identified. The study will use data from the Optum Research Database (ORD), a claims database containing approximately 14 million commercial enrollees and 4 million Medicare-advantage enrollees. The date of the first prescription of either pirfenidone or nintedanib will be assigned as index date. Two separate cohorts will be created - 1) pirfenidone initiators, and 2) nintedanib initiators, and all outcomes will be assessed in the 12 months post-index period. A 12-month time-period prior to the index date will be used as the baseline period for determining the characteristics of patients in both cohorts. To allow for a 12-months baseline and follow-up periods for all patients, the span of data will be from 10/01/2013 to 09/30/2022. (Figure 1)

[figure not shown]

Figure 1 Study Design Schematic

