9.2.2 Study population

For the primary study objective, patients included in the cohort need to meet the following criteria:

- Presence of at least one pirfenidone or nintedanib prescription during the identification period (the date of first prescription for pirfenidone/nintedanib is the index date)
- Evidence of IPF: patient with at least one inpatient or two outpatient claims (>14 days apart) with a diagnosis code for IPF (ICD-10-CM: J84.112; ICD-9-CM: 516.31) during the study period (10/01/2013 to 09/30/2022)
- At least 18 years old at the index date
- Have at least 12 months of continuous enrollment in the health plan during pre-index period, and at least 6 months of continuous enrollment in post-index period (for 12-months analysis, patients would be required to have 12 months post-index continuous enrollment)

Exclusion criteria include the following:

- Any history of lung transplant during the 12-months pre-index/baseline period
- Any claims for a skilled nursing facility, a long-term care facility or hospice care during the 12-month pre-index period
- Evidence (≥2 ICD-9-CM or ICD-10-CM diagnostic codes on different dates) of non-IPF chronic fibrosis ILD or connective tissue diseases during the 12-months pre-index period. The following conditions will be excluded: autoimmune, or connective tissue diseases (i.e., rheumatoid arthritis (RA), systemic lupus erythematosus (SLE), dermatopolymyositis, systemic sclerosis, Sjogren's syndrome, and mixed connective tissue disease (CTD)), sarcoidosis, and hypersensitivity pneumonitis).
- Missing demographic information (i.e., age or sex)

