9.7 DATA ANALYSIS

9.7.1 Main analysis

Baseline characteristics for the pirfenidone and nintedanib cohorts will be reported as frequencies with percentages for categorical data, and means with standard deviations (SD), and median with interquartile range will be reported for continuous variables. We will compare the baseline characteristics using Student's T-test or Wilcoxon rank-sum test for continuous variable, and chi-square test for categorical variable

Average daily dose during first 6 months and 12 months after drug initiation will be reported as means with standard deviations (SD), and median with interquartile range. Six months and 12-months daily dose categories will be presented as frequencies with percentages. Incidence of dose reduction will be reported by month of occurrence (using month 2 and onwards) and reported as frequencies with percentages. Time to drug dose reduction will be reported in months (mean (SD)). Drug discontinuation will be reported as frequencies with percentages, and time to drug discontinuation will be reported in months (mean (SD)). As this is a descriptive study, there will be no multivariable adjustment and/or direct comparison of outcomes between the pirfenidone and nintedanib cohort.

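### Mean time to discontinuation is taken only over patients who stop within 12 months, and mean time to dose reduction appears to be too; neither figure measures how fast patients stop or reduce.

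*Combined protocol and SAP*

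**What the plan says.** For discontinuation, section 9.3.2.2 defines the time variable and who contributes to it: "time to discontinuation will be calculated as time between date of discontinuation and index date (only for patients who discontinue the drug". The event date is set in the same section: "The date of last fill plus the days of supply for the fill (typically 30 days) will be designated as date of discontinuation". Section 9.7.1 gives the summary, "time to drug discontinuation will be reported in months (mean (SD", and the abstract repeats it.

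For dose reduction, section 9.7.1 says "Time to drug dose reduction will be reported in months (mean (SD". It does not say which patients enter that mean.

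The window comes from section 9.1: "all outcomes will be assessed in the 12 months post-index period". Section 9.2.2 requires 6 months of continuous enrolment after index, and adds that "for 12-months analysis, patients would be required to have 12 months post-index continuous enrollment".

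The only censoring rule, "with patient censored at the date of drug discontinuation, or end of 12 months", stands under the average daily dose calculation in section 9.3.2.1. No Kaplan-Meier curve, cumulative incidence function, median allowing for censoring, or restricted mean is planned.

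Two other outputs bear on timing. Section 9.3.2.2 plans the percentage who discontinue in the first 6 and the first 12 months. Section 9.7.1 plans dose-reduction frequencies by month, from month 2.

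**The concern.** A mean over patients who had the event inside a fixed window is a conditional quantity: given that a patient stopped within 12 months, when did that happen? Patients still on drug at month 12 contribute nothing, although they are the ones with the longest times. The figure can therefore stay almost unchanged while the share of patients who stop changes greatly, and it can move in the wrong direction.

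Discontinuation patterns are the secondary aim and dose-reduction patterns are part of the primary aim (section 8). A result of 5 or 6 months is easily read as typical time on drug, when most of the cohort may never have stopped. The two drugs' means will also be seen together. Section 7 says the study may show decision makers how the dosing of the two drugs differs, and section 9.7.2 would repeat the outcomes in matched cohorts if baseline characteristics differ.

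**Working it through.** The documents state no event rate, expected time to event or sample-size calculation, so there is no planned figure to reproduce. All risks and hazard shapes below are assumptions. The 12-month window and the events-only rule come from sections 9.1 and 9.3.2.2.

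**Formula.** Let S(t) be the proportion without the event at month t, p = 1 − S(12), and RMST the area under S from 0 to 12. Then

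mean among events = [RMST − 12(1 − p)] / p.

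With a constant hazard λ = −ln(1 − p)/12, RMST = p/λ, so the mean is 1/λ − 12(1 − p)/p.

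Example, p = 0.10: λ = 0.10536/12 = 0.00878, and the mean is 113.89 − 108 = 5.89 months. For p = 0.80: λ = 1.60944/12 = 0.13412, and the mean is 7.46 − 3.00 = 4.46 months.

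**1. Constant hazard, 12-month window (months).**

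| 12-month risk | Planned mean | RMST, all patients |
|---|---|---|
| 10% | 5.89 | 11.39 |
| 20% | 5.78 | 10.76 |
| 40% | 5.49 | 9.40 |
| 60% | 5.10 | 7.86 |
| 80% | 4.46 | 5.96 |

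From 10% to 80% the hazard rises 15.3-fold (1.60944/0.10536). The planned mean moves by 5.89 − 4.46 = 1.43 months; the RMST moves by 11.39 − 5.96 = 5.43 months.

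**2. Windows nearer the plan's definitions.** A discontinuation is dated at the end of the last supply, so month 1 is about the earliest possible date. For dose reduction, "Patients will be required to have the dose reduction for at least for 60 days", and counting starts at month 2; I took months 2 to 11. If events fall between months a and b with constant hazard and risk p by b, the mean is a + (b − a)/12 times the value in the table.

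- Months 1 to 12: 1 + (11/12)(5.89) = 6.40 at 10% risk; 1 + (11/12)(4.46) = 5.08 at 80%.
- Months 2 to 11: 2 + (9/12)(5.89) = 6.42 at 10%; 2 + (9/12)(4.46) = 5.34 at 80%.

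The range stays narrow.

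**3. Same hazard, different window.** Keep λ = −ln(0.6)/12 = 0.0426 (40% risk at 12 months) and change only the window. The mean is 2.87, 5.49, 9.99 and 13.57 months for windows of 6, 12, 24 and 36 months.

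**4. Shape of the hazard.** With Weibull S(t) = exp(−λt^k) and λ = −ln(1 − p)/12^k:

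| Shape k | p = 20% | p = 40% | p = 60% |
|---|---|---|---|
| 0.5 (early) | 3.78 | 3.50 | 3.12 |
| 1.0 (constant) | 5.78 | 5.49 | 5.10 |
| 1.5 (late) | 7.00 | 6.74 | 6.38 |

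Shape moves the mean by more than 3 months; tripling the risk at a fixed shape moves it by less than 1.

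**5. Wrong order.** A cohort with 60% risk and k = 1.5 has mean 6.38. One with 20% risk and k = 0.5 has mean 3.78. The drug stopped three times as often looks slower. The RMST orders them correctly: 8.63 against 10.36 months.

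A second case uses a hazard of 0.05 per month to month 6 in both cohorts, then either 0.05 or 0.005. The 12-month risk is 45% or 28%, and the mean among events is 5.40 or 3.33. Fewer patients stop, yet the mean is shorter. The RMST is 9.02 or 9.56 and again orders them correctly.

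**The case against.** The strongest reply is that the aim is answered elsewhere. The planned percentages at 6 and 12 months count patients still on drug, so a 10% cohort and a 50% cohort would be plainly different beside their similar means. Dose reduction is reported month by month. With full enrolment required within each window, a Kaplan-Meier estimate at month 6 or 12 in that same sample would equal the planned percentage. This stands. A reader might infer that the plan gives no information on speed, and the documents do not support that. What Kaplan-Meier adds is the course between the two landmarks, confidence intervals, and use of patients who disenrol between months 6 and 12.

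A reader might also infer that the window alone fixes the mean, or that the mean hides a many-fold difference in median time on drug. Neither is supported. Near-insensitivity to the rate depends on a roughly constant hazard; with early or late clustering the mean does carry information on when stopping occurs among those who stop. Medians implied by low risks (78.9 months at 10%, under constant hazard) lie far beyond the window, and no method applied to these data could recover them. The fair comparators are the 12-month risk and the RMST.

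Third, the events-only restriction is written for discontinuation alone. For dose reduction it is an inference: a simple mean has no value to assign to a patient without the event, and no other handling is stated.

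Finally, the study is descriptive, with no direct outcome comparison planned, and section 9.3.2.2 does state the restriction. That lowers the stakes. But the abstract and section 9.7.1 omit the restriction where the statistic is specified for reporting.

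**Conclusion.** The point holds for the two time-to-event summaries and no further. Each is, expressly or by implication, a mean among patients with the event inside 12 months. Under assumed constant hazards, risks from 10% to 80% give means of only 5.9 to 4.5 months. Under assumed Weibull shapes of 0.5 to 1.5 and risks of 20% to 60%, the mean runs from 3.1 to 7.0 months, driven mostly by shape, and the order of two drugs can reverse. These sizes are illustrations, since the documents give no rates. That the mean excludes patients without the event follows from the definition and needs no assumption.

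The planned percentages and monthly frequencies remain valid and limit the harm. The change should be made, but the primary incidence outcome does not depend on it.

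**What to change.** In sections 9.3.2.2 and 9.7.1, and in the abstract to match:

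- **Discontinuation.** Add a Kaplan-Meier curve from index for each cohort in the 6-month-enrolment sample, censoring at disenrolment or month 12. Report the 6- and 12-month probabilities with 95% CI and the 12-month restricted mean, with the median only if it is reached. State how a refill gap that is cut short by disenrolment or by month 12 is classified.
- **Dose reduction.** Add the cumulative incidence from index for each cohort, with discontinuation before any reduction as a competing event. State the denominator of the time-to-reduction mean.
- **Means.** If they are kept, label them 'among patients with the event within 12 months' wherever they appear, and do not present them as typical time on drug.

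The planned percentages and monthly frequencies stay as they are. The cost is protocol wording and a little more analysis per cohort, using index, event and enrolment dates that the plan already needs.
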